## **8. Sample Size Determination**

The planned analysis for the primary outcome is a three-arm comparison of 24-hour opioid consumption. Based on retrospective data reporting 24-hour hydromorphone consumption of  $4.5 \pm 2.9$  mg after PENG block, a conservative standardized effect size of 0.35 was assumed. With  $\alpha = 0.05$  (two-tailed), power of 80%, and three groups, the required sample size was 81 patients. Allowing for approximately 15% attrition, the final target sample size was 93 participants (31 per group).

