### **11.5 Primary Outcome Analysis**

The primary outcome, total morphine consumption in the first 24 postoperative hours, will initially be assessed for normality. If the distribution is non-normal, the primary analysis will use the Kruskal–Wallis test to compare the three groups. If the overall test is significant ( $P < 0.05$ ), pairwise comparisons between groups (PENG vs AQLB, PENG vs Control, AQLB vs Control) will be conducted using Mann–Whitney U tests with

Bonferroni-adjusted significance thresholds. Median differences and 95% confidence intervals will be reported when appropriate.

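### The target of 93 does not cover 15% attrition from a requirement of 81: it covers 12 losses (12.9%), a minor inconsistency in Section 8

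*Combined protocol and SAP*

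**What the plan says.** Section 8 (Sample Size Determination) bases the calculation on a three-arm comparison of 24-hour opioid consumption. It says that "a conservative standardized effect size of 0.35 was assumed", but does not name the type of effect size. With a two-sided 5% level and 80% power, it concludes that "the required sample size was 81 patients", which is 27 per group under the 1:1:1 allocation in Section 3. It then adds an allowance for loss: "Allowing for approximately 15% attrition, the final target sample size was 93 participants (31 per group". The formula for the allowance is not given.

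Three later sections determine what a lost patient does to the analysed number. Sections 11.1 and 11.2 limit the primary analysis to randomised patients who receive their allocated intervention and have primary outcome data. Section 11.3 plans a complete-case analysis without imputation.

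**The concern.** Attrition is normally understood as a share of the patients enrolled. To keep a required number after a loss of 15%, that number is divided by 0.85. Multiplying it by 1.15 gives a smaller target, and 93 is what the multiplication yields. Under the analysis rules in Sections 11.1 to 11.3, a patient without outcome data leaves the analysis and nothing replaces the lost information. The attrition allowance is therefore the only protection for the analysed sample size.

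At stake is whether Section 8 can be quoted as it stands. It implies that the trial can lose about 15% of its patients and still have the number it says it needs. If that sentence is carried into the trial report, it claims slightly more than the design provides.

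**Working it through.** **Inputs, all from Section 8 unless noted**

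- Required evaluable patients: 81 (27 per group).
- Attrition: about 15%.
- Target: 93 (31 per group).
- Effect size: 0.35, type not stated.
- Level and power: 0.05 two-sided and 80%; three groups, with equal allocation from Section 3.

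**Step 1: reproduce the 81.** Read 0.35 as Cohen's f in a one-way F test with three groups. Power is then the probability that a noncentral F variable with 2 and N − 3 degrees of freedom and noncentrality N × f² exceeds the 5% critical value. Here f² = 0.1225, so the noncentrality is 9.92 at N = 81. Power is 79.6%, close enough to the stated 80% to count as a reproduction. Strictly, 80% is first reached at N = 82, or at 84 with equal groups. Reading 0.35 instead as a standardised difference between two means gives 129 per group, which does not fit 81 in total. Cohen's f is therefore the better-fitting reading, but it remains an assumption.

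**Step 2: reproduce the 93.** 81 × 1.15 = 93.15, and per group 27 × 1.15 = 31.05. Both match the plan. That this was the route taken is inferred from the match.

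**Step 3: apply the stated attrition.**

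- Patients left from 93 after 15% loss: 93 × 0.85 = 79.05, so 79, which is 2 below 81.
- Target needed to keep 81: 81 / 0.85 = 95.3, so 96 (32 per group). Check: 96 × 0.85 = 81.6.
- Largest loss that keeps 81: 93 − 81 = 12, and 12 / 93 = 12.9%.

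The shortfall does not depend on Step 2, because 93 × 0.85 is below 81 however 93 was obtained.

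**Step 4: power at each number analysed** (f = 0.35, level 0.05, groups treated as equal in size)

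| Patients analysed | How it arises | Power |
|---|---|---|
| 79 | 93 with 15% loss | 78.5% |
| 81 | the stated requirement; 93 with 12 losses | 79.6% |
| 82 | first number to reach 80% | 80.1% |
| 93 | no loss | 85.3% |

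The cost of the slip at 15% attrition is 79.6 − 78.5 = 1.1 percentage points. The remaining 0.4 points below 80% were already there at 81 and have nothing to do with attrition.

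**The case against.** The best defence is that this hardly matters, and most of it stands.

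- **The wording is approximate.** Section 8 says about 15%, and the 12 extra patients are 14.8% of 81 (12 / 81). Adding a percentage to the required number is a common, looser convention. This explains the figure. It does not make 79 equal to 81 when the percentage is read as a share of those enrolled.
- **The loss may never reach that level.** The outcome is morphine given over 24 hours in hospital, envelopes are opened only after induction (Section 9), and Section 11.3 expects little missing data. Any loss of up to 12 patients keeps at least 81, and with no loss power is 85.3%. This stands, although withdrawals under Section 4.3 and the rules in Sections 11.1 and 11.2 can still remove patients.
- **The effect is small.** Two patients and 1.1 points of power would not change how a null result is read. This also stands.

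Two stronger readings are tempting, and the documents support neither.

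- A reader might infer that the attrition slip is why the trial misses 80% power, or that the trial is materially underpowered. On the reading that reproduces 81, that number itself gives 79.6%, and the slip adds only 1.1 points, and only if loss reaches 15%.
- A reader might infer a further loss of power because Section 11.5 says "the primary analysis will use the Kruskal–Wallis test to compare the three groups". That statement is conditional on a non-normal distribution. The usual efficiency factor of 0.955 for the rank test against the F test applies to normal data, which is the case in which the plan does not call for the rank test. For skewed or heavy-tailed data the rank test can be the more efficient one, so even the direction of any change is unknown. No rank-test power figure belongs in this point.

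**Conclusion.** Section 8 is wrong as written, but the error is minor. A target of 93 does not preserve 81 patients at 15% attrition: it leaves 79, and it protects 81 only up to 12 losses (12.9%). This part is certain, since it uses only the plan's own figures and the usual meaning of attrition as a share of those enrolled.

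The consequence for power is about 1.1 percentage points (79.6% to 78.5%). That figure is less certain, because it assumes that 0.35 is Cohen's f and that the test is a three-group one-way F test. Section 8 names neither, and Section 11.5 specifies a test only for the non-normal case. The case for correcting the text rests on the clear inconsistency and the negligible cost of removing it, not on a material loss of power.

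**What to change.** Keep the target of 93 and restate Section 8 in one of two ways:

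- 93 randomised patients cover about 13% attrition and leave 81 evaluable, with about 79.6% power; or
- at 15% attrition, 93 randomised patients leave 79 evaluable, with about 78.5% power.

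In either case, name the effect size as Cohen's f and the test as a one-way F test, if that is what was used. If something else was used, give the measure and method so that 81 can be reproduced, and recompute the power figure on that basis.

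The cost is a change of wording in one section. The stated attrition or the stated power becomes slightly less favourable. No patients are added, and the design and analysis do not change.

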## **9. Randomization, Allocation Concealment, and Blinding**

Randomization is based on a computer-generated sequence allocating patients to the three study groups in a 1:1:1 ratio. Allocation concealment is achieved using serially numbered, opaque, sealed envelopes prepared by a study coordinator not involved in patient care. Envelopes are opened only after induction of anesthesia. The anesthesiologist performing the block opens the envelope, prepares and administers the assigned intervention, and has no role in postoperative assessment. Patients, surgeons, ward staff, and outcome assessors are blinded to group assignment. Unblinding is permitted only if necessary for urgent clinical management, and the reason and timing are documented.

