### **3. Study Design**

This is a prospective, randomized, double-blind, parallel-group clinical trial with three arms (PENG, AQLB, and Control) with equal allocation (1:1:1). The study is conducted at a single tertiary university hospital (Orthopedic Surgical Theater, Cairo University Hospital). Patients and outcome assessors are blinded to group assignment; the anesthesiologist performing the block is not involved in postoperative assessments.

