## 6.2 Study Arms

### 6.2.1 PENG Block Group

After induction of general anesthesia and before surgical incision, patients in the PENG group are placed supine. A low-frequency curvilinear ultrasound probe (2–5 MHz) is positioned transversely over the anterior inferior iliac spine and rotated approximately 45° counter-clockwise along the pubic ramus. Key sonoanatomy includes the iliopubic eminence, iliopsoas muscle/tendon, and femoral nerve and vessels. A 22-G, 50 mm nerve block needle is inserted in-plane from lateral to medial to reach the fascial plane between the iliopsoas fascia and the pubic ramus, under the iliopsoas tendon. After negative aspiration and a 1 mL saline test injection, 30 mL of local anesthetic mixture (29 mL 0.25% bupivacaine plus 1 mL containing 4 mg dexamethasone) is injected with visualization of appropriate spread.

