### 6.2.2 Anterior Quadratus Lumborum Block (AQLB) Group

After induction of general anesthesia, patients assigned to the AQLB group are positioned in the lateral decubitus position with the operative side up. A low-frequency curvilinear ultrasound probe is placed horizontally above the iliac crest to visualize the transverse process, psoas major, erector spinae, and quadratus lumborum muscles. A 22-G, 50 mm needle is advanced in-plane from posterior to anterior into the fascial plane between quadratus lumborum and psoas major. Following hydro-localization with 1 mL

saline, 30 mL of 0.25% bupivacaine with 4 mg dexamethasone (29 mL + 1 mL) is injected in this plane.

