### **6.5 Definition of Time to First Ambulation and Hospital Discharge**

Time to first walk is defined as the interval between the end of surgery and the time at which the patient can take at least three steps with a walker under physiotherapist supervision. Length of hospital stay is defined as the number of days from surgery until hospital discharge as decided by the orthopedic surgeon.

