## **10. Data Collection and Management**

Data are recorded on pre-designed case report forms by trained staff. Source documents include anesthesia charts, PACU and ward observation charts, medication administration records, and physiotherapy notes. Data are entered into a password-protected electronic database with double-entry verification. Only authorized investigators have access to the final dataset, which is stored in de-identified form for at least five years after study completion.

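### Surgeons and ward staff are declared blinded, but the described procedures do not secure it, and the surgeon decides length of stay

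*Combined protocol and SAP*

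**What the plan says.** Two sections describe who is blinded. Section 3 says "Patients and outcome assessors are blinded to group assignment; the anesthesiologist performing the block is not involved in postoperative assessments". Section 9 goes further: "Patients, surgeons, ward staff, and outcome assessors are blinded to group assignment".

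The procedures that bear on this are:

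- **Timing (section 9).** "Envelopes are opened only after induction of anesthesia".
- **PENG (section 6.2.1).** "After induction of general anesthesia and before surgical incision, patients in the PENG group are placed supine". The probe is placed at the front of the pelvis.
- **AQLB (section 6.2.2).** After induction, "patients assigned to the AQLB group are positioned in the lateral decubitus position with the operative side up". The probe is placed above the iliac crest and the needle enters from behind.
- **Control (section 6.2.3).** No block is given. A sham dressing is allowed as an option, with the stated aim of keeping the blind.
- **Records (section 10).** "Source documents include anesthesia charts, PACU and ward observation charts, medication administration records, and physiotherapy notes".
- **Discharge (section 6.5).** Length of stay runs from surgery "until hospital discharge as decided by the orthopedic surgeon". No discharge criteria are listed. Section 7.2 makes length of stay a secondary outcome.

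**The concern.** Blinding is a property that a reader uses to judge bias, so each group named as blinded needs a procedure that keeps it so. For patients this is plausible, because they are anesthetised when the block is given. For the assessors, the protocol at least bars the person who gives the block from postoperative assessment. For surgeons and ward staff it describes little beyond the assertion itself.

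The surgeon matters most, because the surgeon's own decision fixes one of the compared outcomes. If the surgeon knows the arm, a small and well-meant shift in discharge timing could appear as a treatment effect. A report that repeats section 9 would give the reader no reason to suspect it.

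**Working it through.** **Step 1. Set each blinded group beside its supporting procedure.**

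| Group | Section 3 | Section 9 | Procedure described |
|---|---|---|---|
| Patients | yes | yes | Block given under general anesthesia; optional sham dressing in Control |
| Outcome assessors | yes | yes | Block operator has no role in postoperative assessment |
| Surgeons | not listed | yes | None specific to them |
| Ward staff | not listed | yes | Optional sham dressing in Control |

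**Step 2. Ask what each group could see if the plan is followed as written.**

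- *Theatre.* Between induction and incision the three arms look different: a lateral turn with an injection, a supine injection, or no procedure. No sham positioning, sham block, screening or waiting period is described.
- *Dressing.* PENG and AQLB use different puncture sites. The sham dressing is optional, its site is not specified, and no common scheme covers both sites in all three arms. One dressing at one site would not make the arms look alike.
- *Records.* Block performance time is a secondary outcome (section 7.2), so the block must be recorded somewhere. Anesthesia charts are source documents. Nothing says that the block record is held apart from charts that others may see.

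**Step 3. Trace which outcomes are exposed.**

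- *Length of stay.* The link is direct, because section 6.5 makes discharge the surgeon's decision.
- *24-hour morphine (primary).* The link is conditional. Section 7.1 counts morphine given in the PACU and on the ward, and section 6.4 triggers a dose by pain score, but section 6.4 does not say who scores or who gives it.

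**Step 4. Illustrate how sensitive length of stay is.** The plan gives no figure for this and no stay distribution, so everything except the arm size (31, section 8) and the Kruskal–Wallis test at 0.05 (sections 11.1 and 11.6) is assumed.

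- Stay in each arm = median × exp(log-SD × Z), with Z standard normal and no true arm effect.
- A fixed delay is added to every Control stay, and stays are rounded to whole days.
- The result is the share of 4,000 simulated trials with P < 0.05.

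With no delay, about 5% of trials are significant in every setting, as they should be. With a half-day delay:

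| Assumed median | log-SD 0.25 | log-SD 0.35 | log-SD 0.5 | log-SD 0.7 |
|---|---|---|---|---|
| 4 days | 46% | 26% | 14% | 10% |
| 7 days | 17% | 11% | 7% | 6% |

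Repeat runs differ by up to about 2 percentage points. At a 4-day median and log-SD 0.35, a delay of 0.25 day gives about 9% to 10%, and a delay of 1 day about 80%.

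**The case against.** The strongest reply is that nothing here shows unblinding. No passage places the surgeon in the room during the block, and none says that the anesthesia chart goes to the ward or is read there. That stands. A reader might infer that the trial was in fact open to surgeons and ward staff, but the documents support only that blinding is declared without a mechanism that would secure it.

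A second tempting inference is that the primary outcome is biased because ward staff score pain and give the morphine. The documents do not say that they do. Section 6.4 names no role, section 10 speaks only of trained staff, and section 9 lists ward staff and outcome assessors separately. Rescue also depends on a numeric score from a patient whose blinding is plausible, which limits staff influence without removing it.

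Third, the plan is not silent on masking. It has the sham dressing, an envelope coordinator outside patient care, a block operator kept out of postoperative assessment, and a rule for documented unblinding. These are real safeguards, but none conceals the positioning in theatre or the block record, and the dressing is optional.

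Fourth, section 3 is a short summary that does not exclude anyone from blinding, so the two lists differ in extent and do not contradict each other. That is fair, though they still need to agree.

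Finally, the simulation imposes the delay. It gives no evidence that any surgeon would delay discharge, and the result depends heavily on the assumed stay.

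**Conclusion.** The point holds as a gap between a stated design property and the procedures meant to deliver it. Followed as written, the plan does not secure blinding of surgeons and ward staff. The outcome clearly exposed is length of stay, one of many secondary outcomes. The primary outcome could also be affected if ward staff score pain or give rescue morphine and learn the arm, but the documents do not establish either condition.

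The size of any bias cannot be computed from the documents. The half-day illustration gives false-positive rates of about 10% to 46% for a 4-day median with log-SD 0.25 to 0.7, and for a 7-day median with log-SD 0.35 (11%). They fall to 6% or 7% if a 7-day median is combined with a log-SD of 0.5 or 0.7. These figures assume 31 per arm, no true effect, and the same delay for every Control patient. They show what a modest shift could do and do not estimate what happened. The matter should be corrected, mainly because it affects how readers judge the trial.

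**What to change.** If the procedures can still be set:

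- Make dressings mandatory and identical at both block sites in all three arms.
- Keep the block record on a separate coded sheet that is available for emergency unblinding.
- Admit the surgical team only after a block interval of similar length in every arm, so that neither the positioning nor the wait reveals the arm.

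The cost is one extra form, additional dressings and a short theatre wait.

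If this is not done, or was not done, limit the blinding claim to patients and outcome assessors in both sections 3 and 9. Report length of stay as a surgeon-decided outcome for which blinding was not assured, and interpret it with that caveat. The past-tense statement on interim analyses in section 11.8 suggests that the trial may already be complete, in which case this second route, which costs only wording, is the one available. Under either route, state who scores pain and who gives rescue morphine, so that a reader can judge whether the primary outcome is exposed.

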## **10. Data Collection and Management**

Data are recorded on pre-designed case report forms by trained staff. Source documents include anesthesia charts, PACU and ward observation charts, medication administration records, and physiotherapy notes. Data are entered into a password-protected electronic database with double-entry verification. Only authorized investigators have access to the final dataset, which is stored in de-identified form for at least five years after study completion.

## **11. Statistical Analysis Plan**

### **11.1 General Principles**

Statistical analyses will be performed using IBM SPSS Statistics (version 28). All randomized participants who receive the allocated intervention and have outcome data will be included in the primary analysis (modified intention-to-treat). Two-sided tests will be used with a significance level of  $P < 0.05$ . Continuous variables will be assessed for normality using the Shapiro–Wilk test and visual inspection of histograms and Q–Q plots. Normally distributed variables will be presented as mean  $\pm$  standard deviation and non-normally distributed variables as median (interquartile range). Categorical variables will be presented as counts and percentages. Adjustment for multiple pairwise comparisons will use Bonferroni correction where applicable.

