#### **4.3 Withdrawal Criteria**

Withdrawal of consent at any time.

Intraoperative events requiring deviation from protocol (e.g., conversion to different surgical procedure).

Significant protocol violations deemed to invalidate study data (to be documented and evaluated case by case).

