#### **6.2.3 Control Group**

Patients in the Control group do not receive a regional nerve or fascial plane block. Analgesia is based on systemic opioids only: intraoperative fentanyl and postoperative morphine as described below. A sham dressing may be applied to mimic a block site and maintain blinding.

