### **7.2 Secondary Outcomes**

To compare intraoperative fentanyl consumption between the three groups.

To compare time to first rescue analgesia postoperatively.

To compare Numeric Pain Rating Scale (NRS) scores at rest and during passive 90° hip flexion at predefined postoperative time points (30 min, 2, 4, 6, 8, 12, 18, and 24 hours).

To assess block failure rate, defined as the requirement for more than one rescue morphine dose in the first postoperative hour.

To compare motor recovery (manual muscle test for quadriceps and iliopsoas, and active hip flexion range of motion) over the first 24 hours.

To compare time to first ambulation and length of hospital stay.

To compare intraoperative hemodynamic profiles (heart rate and mean arterial pressure).

To compare the incidence of block-related complications and morphine-related adverse events (e.g., nausea/vomiting, respiratory depression, hypotension, falls).

To compare block performance time and surgical duration between groups.

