### **11.2 Analysis Populations**

The Full Analysis Set (FAS) includes all randomized participants who receive the allocated intervention and provide at least one primary outcome measurement. The Per-

Protocol Set (PPS) includes participants without major protocol deviations that could influence the primary outcome. The primary analysis will be performed on the FAS; sensitivity analyses may be repeated on the PPS if protocol deviations occur.

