## **11.7 Subgroup and Sensitivity Analyses**

No formal subgroup analyses are pre-specified. Exploratory analyses may examine outcomes by sex, ASA class, or age category (e.g., 65–74 vs  $\geq 75$  years), clearly labeled as post-hoc. Sensitivity analyses may be performed excluding protocol deviations or extreme outliers in morphine consumption to evaluate the robustness of the primary findings.

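### The primary analysis set drops patients who did not get their assigned block, a condition that falls mainly on the two block arms, and no planned analysis keeps everyone as randomised.

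*Combined protocol and SAP*

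**What the plan says.** Section 11.1 sets the primary analysis: "All randomized participants who receive the allocated intervention and have outcome data will be included in the primary analysis (modified intention-to-treat"). Section 11.2 agrees: "The Full Analysis Set (FAS) includes all randomized participants who receive the allocated intervention and provide at least one primary outcome measurement". It then says: "The primary analysis will be performed on the FAS; sensitivity analyses may be repeated on the PPS if protocol deviations occur". Section 11.7 adds: "Sensitivity analyses may be performed excluding protocol deviations or extreme outliers in morphine consumption to evaluate the robustness of the primary findings". Section 11.3 uses complete cases without imputation.

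Four other places bear on who can fall out of the set:

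- Section 6.2.3: "Patients in the Control group do not receive a regional nerve or fascial plane block".
- Section 9: the envelope is opened after induction by the anesthesiologist who then carries out the allocation, so that person knows the arm when a block is given or not given.
- Section 4.3 lists among the grounds for withdrawal: "Significant protocol violations deemed to invalidate study data (to be documented and evaluated case by case").
- Section 7.2 has as a secondary outcome: "To assess block failure rate, defined as the requirement for more than one rescue morphine dose in the first postoperative hour".

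**The concern.** Whether a patient gets the assigned block is settled after randomisation, by someone who knows the arm, and the answer decides entry to the primary set. A PENG or AQLB patient can fail the condition because the block was not given or, depending on how receipt is read, not finished. A Control patient can fail it essentially only by being given a block in error. If patients whose block was not done differ in morphine need, the block arms lose them while Control keeps their counterparts. Each block-versus-Control comparison is then biased. A bias in favour of the blocks is plausible but not established.

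Two gaps make this harder to control. Receipt is not defined for a partial injection or for Control. The individual judgements allowed by 4.3 need not be made blind to arm and outcome, and 4.3 does not say whether a patient withdrawn on that ground leaves the FAS.

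**Working it through.** **1. Who can leave the primary set**

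| Event after the envelope is opened | PENG or AQLB | Control |
|---|---|---|
| Block not given | Out | Cannot occur |
| Block started, not completed | Unclear: receipt undefined | Cannot occur |
| Block given, did not work | Stays in (block failure is an outcome, 7.2) | Cannot occur |
| Wrong block, or block given in error | Out | Out |
| No morphine data | Out | Out |

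The asymmetry therefore comes from blocks not given and possibly from blocks not completed. Blocks that were given and failed are not part of it.

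**2. Is there a wider analysis anywhere?** The sets are the FAS (primary), the PPS (narrower, optional) and the 11.7 exclusions (narrower, optional). None is wider than the FAS.

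**3. The plan's own figure (section 8).** Read 0.35 as Cohen's f with three groups and alpha 0.05. One-way ANOVA power from the noncentral F, with noncentrality N × f² = 81 × 0.1225 = 9.92, is 79.6% at N = 81. The smallest total reaching 80% is 82, so the stated 81 is reproduced closely. 81 × 1.15 = 93.15 gives the target of 93, where power is 85.3%. These figures do not bear on the concern, but they support the f reading used in step 6.

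**4. Possible size of the bias.** From the plan: 31 per arm, Kruskal–Wallis at 0.05, then Mann–Whitney at 0.05/3 = 0.017 only if the overall test is significant. Assumed: k patients in every arm have morphine use shifted by s SD and are deleted from both block arms only; there is no true effect. Data are normal or lognormal (log-SD 0.8), with 40,000 runs per row. The false difference in means is k × s / 31.

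| k of 31 | s (SD) | False difference (SD) | Overall error, normal / lognormal | Gated block-versus-Control error, normal / lognormal |
|---|---|---|---|---|
| 3 | 0 | 0 | 0.048 / 0.048 | 0.014 / 0.014 |
| 1 | 1 | 1 × 1/31 = 0.03 | 0.049 / 0.049 | 0.015 / 0.014 |
| 3 | 1 | 3 × 1/31 = 0.10 | 0.056 / 0.062 | 0.018 / 0.022 |
| 5 | 1.5 | 5 × 1.5/31 = 0.24 | 0.093 / 0.111 | 0.037 / 0.046 |

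If non-completion instead occurs at random per patient (12,000 runs, normal data), the overall error with exclusion is 0.059 at 10% and +1 SD, and 0.104 at 16% and +1.5 SD. With everyone kept as assigned it is 0.044 and 0.045.

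**5. A different exclusion model.** Drop the patients in each block arm who rank highest on a risk score correlated rho with morphine use (4,000 runs, simulation error 0.3 to 0.5 points). With rho = 0 there is no bias. With rho = 0.5, dropping 2 or 5 of 31 gives a false difference of about 0.07 or 0.14 SD and an error of 6.0% or 7.7%. With rho = 0.8 and 5 dropped, these are 0.23 SD and about 14%. Keeping all patients gives about 5%.

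**6. Cost of keeping everyone.** If the two blocks work equally well, d = f × 3/√2 = 0.35 × 2.121 = 0.742. If patients without a block get no benefit, d becomes 0.742 × 28/31 = 0.67 with 3 of 31 not blocked, and 0.742 × 26/31 = 0.62 with 5 of 31. At 10% non-receipt and no shift (6,000 runs), Kruskal–Wallis power is 0.81 with exclusion and 0.73 with all kept. In the shifted settings, power with all kept is 0.70 (10%, +1 SD) and 0.58 (16%, +1.5 SD).

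**The case against.** The strongest reply is that the route to bias is narrow. Envelopes are opened only after induction, so dropout and cancellation before surgery precede disclosure of the arm. Section 4.2 already excludes allergy, coagulopathy, neuropathy and puncture-site infection. Few blocks may go undone, and the simulated harm is slight unless the assumptions are extreme. This stands as an argument about size. It does not supply an analysis that would show the bias if it arose.

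The outcome is also bounded: section 6.4 allows 0.3 / 0.05 = 6 boluses in 24 hours. With 0 to 6 boluses (assumed mean 3, 4 or 5, SD 1.5, weight 72 ± 10 kg), the 5-of-31 case gives an overall error of 0.066 to 0.084 and a false difference of 0.13 to 0.19 SD. The 3-of-31 case gives 0.052 to 0.058. The cap trims the worst case but does not remove it.

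On cost, the fall from 0.81 to 0.73 assumes no shift, which is the setting without bias. Where bias exists the power price is higher, as step 6 shows. That is correct and should be weighed.

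Finally, one mandatory as-assigned sensitivity analysis would close the gap without redefining the primary set, and retaining patients converted to another operation adds people who did not have the procedure under study. The first is a workable minimum. It would still leave the headline result on the selected set. On the second, conversion is known only after randomisation, so those patients belong in the as-assigned comparison and can be left out in a sensitivity analysis.

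**Conclusion.** The concern holds on the text. Sections 11.1 and 11.2 agree, so the restriction is the plan and not a slip, and calling it modified intention-to-treat does not restore the randomised comparison. The size cannot be derived from the documents. It is nil if patients without a block are typical. It is about one percentage point of overall error in a moderate case (0.048 to 0.056, or 0.062 with skewed data). In the extreme shift case the error is 0.093 to 0.111 for uncapped data and 0.066 to 0.084 with the cap; the strongest selection model in step 5 gives about 14%. The share excluded, the shift and the correlation are all assumptions. The point is worth correcting because the change is small, but it does not by itself invalidate the trial.

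**What to change.** - **Sections 11.1 and 11.2:** define the FAS as all randomised patients (envelope opened) with 24-hour morphine data, analysed in the assigned arm whether or not the block was given or completed. Patients without morphine data remain a separate missing-data matter that can affect all arms.
- **Section 4.3:** state that intraoperative events and protocol violations neither end collection of 24-hour morphine data nor remove the patient from the FAS. Only withdrawal of consent to use the data does.
- **Sensitivity analysis:** keep the treated-only set under its own name, define receipt in advance for each arm (including partial injection), and have any individually judged exclusion decided blind to arm and outcome. Report non-receipt by arm.

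The cost is wording in three sections. Medication administration records are already a source document (section 10), but no section says collection continues after withdrawal, so 4.3 must say so. The statistical cost is the dilution in step 6, which is negligible if nearly all blocks are completed.
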